13.13 CONCOMITANT MEDICATIONS

Any medications to be taken during the study must be approved by the investigator. The following medications should not be used during treatment with STS:

- 1. MAO inhibitors (e.g., phenelzine (Nardil®), tranylcypromine (Parnate®), selegiline (Eldepryl®), etc.)
- 2. Selective serotonin reuptake inhibitors (SSRI; e.g., fluoxetine, paroxetine, sertraline, fluvoxamine, citalopram)
- 3. Psychotropic medications
- 4. Centrally active anticholinergics
- 5. Anticonvulsants (case by case)
- 6. Antiparkinsonian agents
- 7. Antidepressants
- 8. Antipsychotics, including lithium carbonate
- 9. Anxiolytics
- 10. Psychostimulants
- 11. Nootropics
- 12. Cerebral enhancers
- 13. Vasodilators
- 14. Benzodiazepine receptor agonists
- 15. Reserpine
- 16. Hypnotics
- 17. Oral neuroleptics, depot neuroleptics, methyldopa, ergot preparations.
- 18. Sympathomimetic medications: e.g., amphetamines, methylphenidate, dopamine, epinephrine, norepinephrine, levodopa, tyrosine, phenylalanine, mazindole tyrosine; OTC and prescription nasal decongestants, and appetite suppressants.
- 19. L-tryptophan, metoclopramide
- 20. Meperidine (Demerol®), dextromethorphan or opiates
- 21. Propoxyphene
- 22. 5-HT receptor agonists (e.g., sumitriptan succinate [Imitrex®], zolmitriptan [Zomig®], serotonergic agonists or antagonists (e.g. cyproheptadine [Periactin®], methysergide [Sansert®])

- 23. CNS active herbal preparations including, but not limited to, St. John's Wort, yohimbine, valerian, kava/kavatrol and gingko biloba
- 24. Any opiate-substitutes (methadone, LAAM, buprenorphine)
- 25. Inhaled or oral beta-agonist or steroid therapy for asthma (due to potential serious adverse interactions with cocaine, e.g., albuterol)
- 26. OTC agonists or allergy medication for respiratory problems (e.g., Primatene Mist).

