TREATMENTS: A STS patch (STS: $1.0 \text{ mg/cm}^2 \times 20 \text{ cm}^2$ patch) or matching placebo patch will be worn for 24 hours and replaced daily for the 8-week duration of the study. All subjects will receive manual-guided psychosocial therapy weekly during the 8 weeks of treatment.

DURATION OF THE STUDY: The total duration of study participation for each subject will be a maximum of 16 weeks consisting of: screening to be completed within 30 days prior to randomization including a 14-day baseline assessment period; double-blind medication (8 weeks); and, follow-up evaluation conducted 4 weeks following completion or termination from the study.

SAFETY ASSESSMENTS: All candidates for study enrollment will have a physical examination, a 12-lead ECG and clinical laboratory studies (blood chemistry, hematology, and urinalysis) performed during screening. During the treatment phase, vital signs will be taken at each visit for the first two weeks and weekly thereafter. Assessments of adverse events (AEs), concomitant medications, and a urine screen for other substances of abuse will be performed weekly. An HIV Risk Assessment Battery will be used to characterize the population HIV risk behaviors (screening and week 8). At treatment week 8, or at the time of study discontinuation, subjects will be evaluated by AE assessment, vital signs, physical examination, clinical laboratory studies, and ECG.

EFFICACY ASSESSMENTS: Success in reduction of cocaine use will be determined by comparing the weekly mean proportion of cocaine non-use days (self-report confirmed or disproved by urine BE level at each study visit) in both treatment groups. Secondary assessments include overall proportion of cocaine non-use days, proportion of successful subjects, the largest number of consecutive cocaine non-use days, weekly mean quantitative urine BE levels, Addiction Severity Index (ASI) score, HAM-D score, Brief Substance Craving Scale (BSCS) score, Clinical Global Impression scores as assessed by the subject (CGI-S) and an observer (CGI-O). ASI is performed during screening and at the first visit of week 5 and at the end of week 8. The BSCS, CGI-S, and CGI-O are performed weekly during the 14-day baseline assessment period and the first visit of each study week. The HAM-D is performed during screening and every two weeks during treatment.

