The investigational drug to be investigated in this study is Selegiline. Selegiline is an irreversible selective inhibitor of monoamine oxidase type B (MAO-B). It is hypothesized that selegiline may affect cocaine addiction through several potential mechanisms of action. Inhibition of MAO-B increases concentrations of dopamine and other neurotransmitters, which may help restore normal levels in subjects whose use of cocaine has disrupted levels of these neurotransmitters. Another hypothesis is that selegiline metabolites may provide a low, but sustained therapeutically effective level of substitution for the stimulating effects of cocaine. There is no evidence that selegiline causes euphoria or dependence. The high degree of MAO-B inhibition achieved is associated with functional increases in dopamine concentrations. Dopamine is thought to be central to the reinforcing effects of cocaine. While dopamine depletion has been associated with chronic cocaine use and withdrawal symptomatology, it is widely accepted that euphoria associated with cocaine use is a result of action at reward pathways via antagonist properties at the dopamine transporter site. Cocaine also inhibits reuptake of the neurotransmitters serotonin and norepinephrine. These actions are thought to underlie cocaine's potent reinforcing properties. With prolonged use, cocaine may deplete these neurotransmitters, affect postsynaptic receptor density, and elicit an overall dysregulation of these neurotransmitter systems. These long-term consequences may account for the post-cocaine dysphoria thought to contribute to relapse.^{1, 2,3}

Pharmacology laboratory studies in humans and animals suggests that selegiline blunts the reinforcing effect of cocaine, while a pilot outpatient clinical trial, with a sustained release oral selegiline, reduced cocaine use.⁴

Selegiline was first tested for cocaine dependence using a sustained-release oral dosage formulation. Initial, protocol-specified analyses of a phase 2, double-blind, placebo-controlled clinical trial showed a trend toward decreased cocaine use. However, subsequent analysis according to FDA's recommendations showed a statistically significant effect of selegiline over placebo. Currently, this is the strongest positive treatment signal seen in clinical trials for cocaine dependence.⁴ However, sustained-release selegiline is no longer available.

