- 2. Individuals with neurological or psychiatric disorders, such as psychosis, bipolar illness, major depression (as assessed by the SCID) and/or current suicidal ideation (as assessed by SCID or HAM-D question #3), organic brain disease, or dementia, which require ongoing treatment or which would make medication compliance difficult. Past history of depression or suicidal attempts (as assessed by history/SCID) will not exclude subjects from participating in the study as long as they don't have a current diagnosis of major depression or suicidal ideation.
- 3. Subjects with serious medical illnesses including, but not limited to, uncontrolled hypertension, significant heart disease (including myocardial infarction within one year of enrollment), angina, cardiovascular abnormality, hepatic or renal disorders, or any serious, potentially life-threatening or progressive medical illness other than addiction that may compromise subject safety or study conduct.
- 4. Individuals mandated by the court to obtain treatment for cocaine-dependence.
- 5. Individuals not seeking treatment for cocaine dependence.
- 6. Individuals anticipating elective surgery within 14 weeks of signing the informed consent form.
- 7. Anyone who in the opinion of the investigator would not be expected to complete the study protocol due to probable incarceration or relocation from the clinic area.
- 8. Individuals with AIDS.

- 9. Individuals with active syphilis that have not been treated or refuse treatment for syphilis (see following note pp.19-20).
- 10. History of neuroleptic malignant syndrome.
- 11. Known or suspected hypersensitivity to selegiline, any monoamine oxidase inhibitor, or PEA.
- 12. Known allergic or chronic dermatologic illness (e.g., psoriasis), that might interfere with the STS absorption or which may be exacerbated by STS patch application.
- 13. Individuals with Hymenoptera allergy that requires carrying prophylactic epinephrine.
- 14. Therapy with a medication that could interact adversely with selegiline, with the time of administration of study agents relative to other medications based on the longest time interval of A, B, or C, below:

A) Five half lives of other medication or active metabolite(s), whichever is longerB) Two weeksC) Interval recommended by other medication's product labeling

Medications that fall into this category include:

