10.3 ADAPTIVE RANDOMIZATION

Adaptive random allocation of subjects to study groups was developed to balance groups with respect to screening prognostic variables. The procedure allocates treatment assignment based on the assignments and prognostic variable levels for all previously enrolled subjects. The treatment groups will be balanced with respect to gender, diagnosis of ADD, historical Self-Report of cocaine use (< 18 or \ge 18 days of use in the last 30 days), and severity of depression (HAM-D score \le 11 or > 11). A new subject will be randomized with a "biased coin" procedure which uses randomization probabilities, favoring the treatment with the deficit enrollment, to improve the balance on group assignment.¹⁰ The randomization process will be performed by computer at CSPCC.

Rationale for ADD as a stratification variable. It has been observed that a relatively high percentage of cocaine abusing or dependent individuals have a current diagnosis of ADD or a past history of ADHD. For example, in one sample of 281 cocaine abusers seeking treatment, 12% of the individuals met DSM-IV criteria for childhood ADHD, and 10% for adult ADD.¹¹ In another report, 35% of 298 treatment-seeking cocaine abusers met DSM-III-R criteria for childhood ADHD.¹² Compared to those who did not have a childhood ADHD diagnosis, those that did, reported more severe substance use, earlier onset of cocaine abuse, and more frequent and intense cocaine use. Other studies assessing the prevalence of ADD in individuals seeking treatment for cocaine abuse or dependence, as well as those assessing the prevalence of cocaine use in subjects seeking treatment for ADD, and evaluating the adult status of children who were treated for ADHD, support the association between ADD and cocaine use. It is possible that cocaine use by some individuals with ADD/ADHD may be an attempt to self-medicate for the disorder. Given the association between ADD/ADHD and cocaine use, as well as preliminary data indicating that selegiline may be effective for the treatment of ADD/ADHD, it is appropriate to balance groups in the present study with respect to a diagnosis of ADD. Individuals who are identified as having ADD as part of the study screening process will be informed of this, and will be encouraged to seek further evaluation and appropriate treatment.

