13.8 MAO-I SAFETY

No significant changes in blood pressure have been observed in the Somerset sponsored clinical trials in depression or in the NIDA clinical pharmacology studies with cocaine and STS. Based on studies performed by Somerset, tyramine dietary restrictions have been removed from STS protocols. In the unlikely event of a hypertensive crisis and/or STS overdose, the transdermal system should be discontinued and the underlying skin washed with soap and cold water to remove any residual investigational agent.

Vital signs will be measured to detect a pressor response in subjects receiving MAO inhibitors. Full reliance should not be placed on blood pressure readings, and the subject should also be observed for clinical signs of a sympathomimetic reaction. Accordingly, clinical judgment should be exercised regarding discontinuation of investigational agent if symptoms such as palpitations, tachycardia, sense of constriction in the throat or chest, or frequent headaches occur during the trial.

Subjects will be instructed to report promptly the occurrence of headache or other unusual symptoms, i.e., palpitations and/or tachycardia, a sense of constriction in the throat or chest, sweating, dizziness, neck stiffness, nausea, or vomiting.

Subjects will be cautioned not to take concomitant medications, whether prescription or OTC medications, without consulting the site investigator or physician designee.

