13.12 SUBJECT WITHDRAWAL

An investigator may terminate a subject if s/he deems it clinically appropriate or for any of the following reasons: 1) significant side effects from investigational agents, 2) serious or unexpected AEs, 3) inability to comply with the study protocol, 4) protocol violation, or 5) serious intercurrent illness. A subject may withdraw from the study anytime s/he wishes. In the event a subject is discontinued from receiving the investigational agent, s/he will be allowed to continue the psychosocial-behavioral treatment with the approval of the investigator.

Any subject who discontinues prematurely, regardless of the reason, will be requested to return for a final visit to perform the necessary procedures and obtain data for end of study/early termination (see section 14.3).

Study participants withdrawn from the protocol secondary to a medical or psychiatric concern will be referred for appropriate treatment. Subjects will be asked to sign a general consent for the release of information to the referred health care. Study staff may request transportation for emergency treatment of a subject if medically appropriate (e.g., for acutely psychotic or suicidal subjects).

All study participants will be encouraged to carry a wallet card that identifies them as a participant in a clinical research study. The card will provide the name and phone number of the site investigator who can be contacted in the event of an emergency. The card will also instruct the non-study physician rendering emergency care to provide information to the site investigator with regards to that care.

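### The barred-drug list stops at the last patch of an irreversible MAO inhibitor, and the week-12 follow-up collects adverse events without concomitant medications

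*Protocol*

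**What the plan says.** **The bar on medications.** Section 13.13 opens with a general rule: "Any medications to be taken during the study must be approved by the investigator". It then gives 26 numbered entries that should not "be used during treatment with STS". They include MAO inhibitors, SSRIs and other antidepressants, psychostimulants, sympathomimetics with nasal decongestants, meperidine and dextromethorphan, propoxyphene, serotonergic agents, L-tryptophan and St. John's Wort. No interval after the last patch is stated. Section 13.8 adds a caution without an end date: "Subjects will be cautioned not to take concomitant medications, whether prescription or OTC medications, without consulting the site investigator or physician designee".

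**The drug.** Section 4: "Selegiline is an irreversible selective inhibitor of monoamine oxidase type B (MAO-B"). Section 4.1 repeats that the inhibition is irreversible.

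**The entry rules.** Exclusion 14 times the patch relative to an interacting drug, "based on the longest time interval of A, B, or C". These are five half-lives, two weeks, and the other drug's labelling. Item 14a asks for eight weeks for MAO inhibitors, naming selegiline, and for SSRIs.

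**Follow-up.** The synopsis says "The total duration of study participation for each subject will be a maximum of 16 weeks", and it counts the four-week follow-up in that total. Section 15.7 collects adverse events up to four weeks after completion or termination. Section 14.4 lists substance use, current drug or alcohol treatment, an impression of the study medication, urine BE and creatinine, and adverse events. It does not list concomitant medications, and neither does 13.7. The last scheduled medication record is at the termination visit (14.3, item 20).

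**The concern.** The protocol treats carry-over as real at entry but says nothing about it at exit. Read literally, 13.13 would let an SSRI, meperidine or a stimulant start the day after the last patch, provided the investigator agrees. The investigator asked to agree has no interval to apply or to pass on to an outside prescriber.

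The question can arise from the protocol's own instructions. Section 13.12: "Study participants withdrawn from the protocol secondary to a medical or psychiatric concern will be referred for appropriate treatment". It can also arise within the eight weeks, because 13.6 lets a subject stop patches and stay in the study.

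The second part concerns attribution. Investigators record the relationship of each adverse event to study treatment (14.6.17), and the medical monitor reviews relatedness (15.5). If palpitations are reported at week 12, a drug begun in the preceding four weeks may be their cause, or may have interacted with STS. No scheduled form would show it.

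**Working it through.** The plan states no figure on this point, so there is nothing to reproduce. The check sets the provisions side by side and counts the schedule.

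**1. Separation at entry against separation at exit**

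| Situation | Interval in the protocol | Source |
|---|---|---|
| Interacting drug, then patch | at least 2 weeks | exclusion 14 B |
| MAO inhibitor (selegiline named) or SSRI, then patch | 8 weeks | exclusion 14a |
| Patch, then any listed drug | none stated | 13.13 |

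The two directions are not mirror images. Exclusion 14 clears the other drug; an exit rule would wait for MAO activity to recover. The closest parallel is the eight weeks after a previous MAO inhibitor. The protocol does not say how long inhibition lasts after the last patch. Its nearest evidence is in 4.3, where the fall in cocaine self-administration in monkeys outlasted the selegiline infusion by several days. So the text supports the need for an interval but does not fix its length.

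**2. Marks in Table 1**

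- Adverse events: 8 treatment weeks + termination + follow-up = 10.
- Concomitant medications: 8 treatment weeks + termination = 9.
- The missing mark is week 12, which agrees with 14.3 and 14.4.

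Medications are reviewed once a week during treatment (14.2). The right comparison is therefore 9 scheduled records up to termination against none afterwards. The 3 × 8 = 24 treatment visits are not the comparator.

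**3. Length of the unrecorded window**

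- Completer: adverse events over 56 + 28 = 84 days, medications over 56 days; 28 / 84 = 33%.
- Illustration, termination at the end of week 4: adverse events over 28 + 28 = 56 days, medications over 28 days; 28 / 56 = 50%.

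These fractions describe the schedule. They do not count people who start an interacting drug, and the document offers no rate for that.

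**4. What the other provisions cover in follow-up**

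| Provision | What it does | What it leaves open |
|---|---|---|
| Approval rule, 13.13 | probably applies, since the synopsis counts follow-up as participation | gives no interval |
| Caution, 13.8 | no end date | gives no interval, schedules no record |
| Adverse events followed to resolution, 15.7 | further contact for subjects with an unresolved event | no medication record required |
| SAE report with medication form, 15.8 | records medications when an SAE occurs | non-serious events |
| Monitoring after withdrawal for an SAE, 15.8 | covers part of the withdrawn group | other withdrawals |
| Weekly review if patches stop but the subject stays, 13.6 and 14.2 | medications recorded through week 8 | no interval after the last patch |
| Follow-up self-report, Table 1 note c | cocaine, opiates, alcohol, nicotine, marijuana | antidepressants, stimulants, decongestants |

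Two gaps remain: no interval after the last patch, and no routine medication record for non-serious events in the last four weeks.

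**The case against.** The strongest reply is that the document does not establish the hazard. It never says how long inhibition persists. The Investigator's Brochure and the appendices, including the one on adverse event reporting, are not at hand. The protocol's own data are reassuring: in 4.4's companion background (Section 4) the tyramine sensitivity factor is 1.82 for the 20 mg patch, against 1.62 for the oral capsule and above 40 for Parnate. Section 4.5 gives preliminary data in 12 subjects with no change in cocaine's cardiovascular effects, and 13.8 reports no significant blood pressure changes. This stands as a limit on severity. It does not remove the point, because those data concern tyramine, cocaine and blood pressure, not SSRIs, meperidine or stimulants. Section 4.2 also notes that in animals, routes avoiding first-pass metabolism can inhibit both MAO types in the brain while peripheral activity is kept.

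Three further objections stand and shape the fix:

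- Fourteen days is only an analogy with exclusion 14 B, and the entry rules would equally suggest eight weeks.
- Extending all 26 entries would be too broad. Item 25, for example, is barred because of cocaine, and a wide bar would burden subjects referred for psychiatric care.
- Blinding adds little, since an investigator can treat every subject as possibly on STS.

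A reader might infer that follow-up is uncontrolled. It is not: the provisions in step 4 of the working probably reach it in part. A reader might also take subjects with ADD as an exposed group, since they "will be informed of this, and will be encouraged to seek further evaluation and appropriate treatment". That advice belongs to screening, and nothing links it to starting a stimulant soon after the last patch.

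**Conclusion.** Both parts hold on the text. Section 13.13 ends its bar with treatment, although the drug is described as irreversible and separation is required at entry. Week 12 collects adverse events with no medication record. The recording gap is explicit in 14.4 and Table 1. The missing interval is also explicit, but its clinical importance is inferred.

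The size is modest: four weeks per subject, or 28 of 84 days for a completer, without a scheduled medication record. A reader might turn this into a number of subjects at risk or a demonstrated interaction. The documents support neither, since they give no rate of starting a listed drug after the last patch and no case of harm. Efficacy analysis and power are unaffected.

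The conclusion assumes that the approval rule reaches follow-up and that the appendices not seen do not already supply an interval or a week-12 medication form. This is a minor safety and recording improvement.

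**What to change.** 1. **14.4 and Table 1:** add concomitant medications with start dates to the week-12 column, or to the telephone contact that 13.7 allows.
2. **13.13, both arms:** extend the bar past the last patch only for entries listed because of MAO-inhibitor interaction. Examples are MAO inhibitors, SSRIs and other antidepressants, psychostimulants and sympathomimetics, meperidine, dextromethorphan and propoxyphene, serotonergic agents, L-tryptophan and St. John's Wort. Leave out entries barred because of cocaine, such as item 25. Set the interval at 14 days or more, or at the figure the Investigator's Brochure supports. Exempt urgent treatment, to be decided by the investigator with the medical monitor.

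The cost is a wording amendment and one existing form at an existing visit or call, with no added visits or subjects. The downside is a short delay in starting a non-urgent interacting drug.
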